6.5.5 ST de-mediation via g-estimation

A g-estimation approach will be implemented on each of the **B x M** imputed complete dataset, to de-mediate the MDS-UPDRS data from the confounding effect of the rescue medication (i.e. ST, Levodopa mainly) on the observed effect of the active randomized treatment (Minzasolmin/UCB0599) to obtain the direct effect of this active treatment.

The basic idea of apply a g-estimation algorithm is to “peel off” the effect of ST on all future MDS-UPDRS observations.

Complete post-MI-MCMC MDS-UPDRS Part I-III sum score, Part III subscale and Part III ePD subscore outcome data will be used in the g-estimation models, both as the dependent variable and as the respective lagged outcomes, i.e. time-varying covariate.

Note that to be conservative, RBI data from participants who discontinued the study for reasons related to randomized treatment will not be ST de-mediated.

In the g-estimation approach, sex (reference = Male), age at formed consent signing (agegrp4, reference = 60-69), and geographic region (reference = Europe) will be included as baseline demographic covariates and carried over time. Baseline/screening data for MDS-UPDRS Part II and DaT-SPECT Striatum SBR (not mean-centered) will also be included as time-varying covariates. Where post-baseline data for these time-varying covariates are missing, a last observation carried forward (LOCF) approach will be applied to impute missing data, both in the case where the variable is not measured at a visit by design, or in the case where it is truly missing (assumes MAR).

Exploratory sensitivity analyses may be run where additional time-varying covariates are included in the g-estimation model as lagged predictors (details to be included in the exploratory analysis plan).

- Prepare dataset for g-estimation 2-step modeling:
 - Set time t to start at 1 up to T (where $T = 10$ visits, Baseline, Month 2 ... Month 18)
 - For each $B \times M$ imputed dataset (including any baseline/post-baseline variables as required), within each participant, lag the following variables over each Visit V_t using SAS functions Lag1, Lag2 to Lag($T-1$), i.e.:
 - S_t , whether a participant initiates ST between V_t and V_{t+1} , set to 1 if yes, set to 0 otherwise (generates lag1S, lag2S ...); once a participant has initiated ST, it is assumed they stay on ST for the remaining of the trial;
 - Y_t , the participant's outcome measured at V_t (generates lag1Y, lag2Y ...)

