 - $L_t(s)$, the participant's time-varying variables measured at V_t (generates e.g. lag1updrs2, lag2updrs2 ...).
 - For each $B \times M$ imputed dataset, carry forward participant's demographics L_1 measured at screening/baseline across all visits (generates e.g. lagSex ...)
 - Exclude baseline rows ($t = 1$) from dataset.
- Step 1: Propensity model - For each $B \times M$ dataset, estimate the participant's propensity score (p_t), i.e. the probability of initiating ST at any post-baseline visit based on outcome using a logistic regression model.
 - Exclude rows corresponding to $V_{t=T}$ (i.e. Month 18), where S_t is not applicable
 - Retain rows where S_{t-1} (lag1S) = 0 (i.e. participants did not initiate ST up to and including V_t)
 - Run a logistic regression of S_t on Y_t , adjusting for:
 - V_t , R (Randomized treatment arm) - Class variables as Fixed effects:
 - Sex, Age group, and Geographic region - Class variables as demographics covariates

- MDS-UPDRS Part II, DaT-SPECT striatum SBR - Continuous variables as baseline covariates
- Use model to predict the p_{st} for each participant at each V_t .
 - Where S_{t-1} (lag1S) = 1 or S_t not applicable, then set $p_{st} = 1$;
- Lag the p_{st} variable within each participant, over each V_t as described in the data preparation section above (lag1PS to lagTPS).
- Step 2: linear structural mean model (LSMM) - For each $\mathbf{B} \times \mathbf{M}$ dataset, estimate the lag effects ψ_g of initiating ST between V_t and V_{t+1} on Y_{t+g} for all possible lags g from 1 to G ($T-1$), assuming ψ_g is time-invariant, by implementing a series of linear regression models and de-mediate the overall lag effects of ST on outcome:

To estimate ψ_1 (example for lag $g = 1$),

- Retain rows Y_{t+1} where S_{t-1} (lag2S) = 0 for $t = 1, \dots, T-1$
- Run a linear regression of Y_{t+1} on 1-lag outcome Y_t (lag1Y), observed ST initiation S_t (lag1S), and propensity score for ST initiation p_{st} (lag1PS), adjusting for:
 - R (Randomized treatment arm) - Class variables as Fixed effects (Visit not included as fixed effect):
 - Sex, Age group, and Geographic region - Class variables as demographics covariates
 - MDS-UPDRS Part II, DaT-SPECT striatum SBR - Continuous variables as baseline covariates
- Set ψ_1 estimate equal to the linear coefficient of S_t (lag1S)

To estimate ψ_g for $g = 2, \dots, T-1$ (generalization to all possible lags)

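### SAP 6.5.5 contradicts itself on whether Part II and DaT-SPECT enter the de-mediation models as current or baseline values, and its row rules leave the lag-9 ST effect inestimable

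*SAP*

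**What the plan says.** SAP 6.5.5 removes the effect of ST in three steps. Step 1 is a logistic model for the probability of starting ST after each visit. Step 2 is a series of linear models for the effect of that start on the score g visits later. Step 3 subtracts those effects.

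**Covariates.** The introductory text states "Baseline/screening data for MDS-UPDRS Part II and DaT-SPECT Striatum SBR (not mean-centered) will also be included as time-varying covariates". For post-baseline gaps, "a last observation carried forward (LOCF) approach will be applied to impute missing data". Data preparation then lags "the participant's time-varying variables measured at V_t (generates e.g. lag1updrs2, lag2updrs2". A further sentence says "Exploratory sensitivity analyses may be run where additional time-varying covariates are included in the g-estimation model as lagged predictors"; the word *additional* suggests that the main model already has such covariates. Yet the adjustment list in Step 1, repeated in Step 2, reads "MDS-UPDRS Part II, DaT-SPECT striatum SBR - Continuous variables as baseline covariates". Lags 2 and above are adjusted in the same way as lag 1. The endpoint itself is used "both as the dependent variable and as the respective lagged outcomes, i.e. time-varying covariate".

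**Rows.** Time runs from 1 to T, "where $T = 10$ visits, Baseline, Month 2 ... Month 18". After the lags are made, the instruction for t=1 is "Exclude baseline rows". Step 1 fits post-baseline visits only. Step 2 runs from t=1 to T-1 at lag 1 and from t=1 to T-g at lag g, with g up to T-1.

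**The concern.** G-estimation recovers the effect of ST only if the reasons for starting it are adjusted for at the time of the decision. Protocol 4.2 ties ST onset to disease progression, and Protocol 6.5.3 ties it to the individual participant's needs. Part II records motor experiences of daily living (Protocol 8.1.1.1), so its value at the visit before ST starts is a plausible driver. The Part III and ePD endpoints contain no Part II items, so adjusting for the endpoint does not supply that information. Two programmers following 6.5.5 could build different models, and one of them would omit a variable that the plan has already prepared.

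The row rules raise a different question: whether Steps 2 and 3 can be executed for every lag that the plan requires.

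These analyses matter because SAP Amendments 3 and 4 introduced de-mediation after more participants than expected had started ST before Month 12. SAP Table 1-2 labels the de-mediated Part III and ePD means key secondary. SAP 6.2 calls them supplementary.

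**Working it through.** The plan states no figure that depends on this specification, so there is none to reproduce. The check sets the instructions side by side, counts intervals, and gives a range for the bias under stated assumptions.

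**1. Covariates.** Time-varying reading: the introductory sentence, the carry-forward rule, the lagged copies such as `lag1updrs2`, and the sentence on additional covariates. Baseline reading: the adjustment lists of Steps 1 and 2, which are the only lines defining what enters the models. No model line calls the lagged copies. The introductory sentence is itself mixed, because it calls baseline/screening data time-varying.

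**2. Where the two readings differ.**
- *Part I-III sum score:* it contains items 2.1 to 2.13 (SAP 5.3), so adjusting for the current outcome already carries Part II.
- *SBR:* scans are planned at Screening, Month 12 and Month 18. Under carry-forward the current value equals baseline at t=1 to 6 (Baseline to Month 10). The readings can differ only for ST decisions after Months 12, 14 and 16, which is 3 of 9 intervals. German participants have no Month 12 scan.
- *Part II with the Part III or ePD endpoint:* the readings differ at every interval after the first. At t=1 the baseline value is the current value.

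**3. Intervals by lag.** T = 10, so there are 9 intervals in which ST can start. Lag g uses t = 1 to 10-g, which is 10-g intervals. With t=1 deleted before Step 1, only t ≥ 2 has a propensity, leaving 9-g.

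| Lag g | 1 | 2 | 3 | 4 | 5 | 6 | 7 | 8 | 9 |
|---|---|---|---|---|---|---|---|---|---|
| Intervals required | 9 | 8 | 7 | 6 | 5 | 4 | 3 | 2 | 1 |
| With a propensity | 8 | 7 | 6 | 5 | 4 | 3 | 2 | 1 | 0 |

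ψ₉ therefore has no data. The Step 2 retention rule at t=1 also needs S₀, which is not defined; at lag 9 this is `lag10S`, while only lags 1 to 9 are generated.

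**4. Who is affected by lag 9.** ψ₉ applies only to the Month 18 score of participants who start ST between Baseline and Month 2. SAP 3.2 gives 10/391 = 2.6% on ST by 3 months in the planning cohort; 10/391 × 450 = 11.5, so about 12 participants. Month 12 is t=7 and needs lags 1 to 6, each of which keeps at least 3 intervals.

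**5. Size of the covariate effect (all inputs assumed).**
- *Lag 1 only:* 450 participants, true ST effect -5, 200 runs per scenario, 31 to 36% on ST by Month 12. With baseline Part II the estimates were -5.03, -4.96, -4.93, -4.87 and -4.71 as Part II's influence on ST start and on later outcome increased. With current Part II they were -5.01 to -5.04. The largest shortfall is 0.29/5 = 6%. Keeping the t=1 rows changed estimates by at most 0.04.
- *All lags, true effect -4, 50 to 60% on ST by Month 18, active arm progressing 35% slower, 300,000 participants:* with baseline Part II the cumulative ST effect was -3.8 to -2.8. That is 1 - 3.8/4 = 5% to 1 - 2.8/4 = 30% too small. Placebo Month 18 means were off by 0.2 to 0.6 points. The worst treatment difference was -3.40 against a true -3.46, and 0.06/3.46 = 1.7%.
- *All lags, true effect -4, 28 to 37% on ST by Month 18, t=1 dropped, 150,000 participants:* with baseline Part II the cumulative effect was -3.7 to -3.1 (8 to 23% too small). Placebo means were off by 0.1 to 0.3 points. The difference was -3.45 to -3.41 against -3.46 (0.3 to 1.4%). With current Part II the cumulative effect was -3.96 to -3.99.

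The 6% and the 30% do not conflict: the first is one lag, the second the sum over lags.

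**The case against.** A reader might infer that the ST effect *is* estimated with avoidable confounding and that deleting the baseline rows adds to it. The documents support neither statement.

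Most of the text favours the time-varying reading, and the baseline label may have been carried over from the imputation text in SAP 6.5.4, where the same two variables are baseline covariates. Confounding from omitted current Part II arises only if the label is what gets programmed. Even then the endpoint at visit t is still adjusted for, SBR hardly changes, and the sum score carries Part II already. The quantity of interest is the treatment difference, which moved by at most 0.06 points in the simulations; SAP 3.3 cites 3.25 points as the minimal important Part III improvement.

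Deleting t=1 is not a confounding mechanism. Baseline values survive as lags on later rows. Because the lag effects are assumed constant over time, ψ₁ to ψ₈ from later intervals still correct the scores of early starters. Inclusion criterion 7a also selects against early starting.

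All of that stands, and it limits the size of the point. It does not remove the contradiction in the lines that define the models, and it does not make lag 9 computable. The ST effect also drives the de-mediated arm means, which SAP 6.5.7 reports.

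**Conclusion.** Two drafting defects stand, and they are separate.

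1. The covariate specification contradicts itself. Followed literally, Steps 1 and 2 leave current Part II out of the Part III and ePD de-mediation. The bias cannot be derived from the documents. Under assumed inputs the ST effect is shrunk by roughly 0 to 30% and the treatment difference by at most about 2%. The consequence for the sum score and for SBR is small.
2. The algorithm cannot be run in full as written. Starts before Month 2 have no propensity, each lag loses one interval, and ψ₉ is inestimable. The reach is the Month 18 scores of about 12 of 450 participants. That count rests on the planning rate: its 3-month window is longer than the interval concerned, but overall ST use in the trial has exceeded planning, so the actual count could differ. Month 12 lags remain estimable.

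The primary analysis, which censors after ST, is unaffected. The correction is still worth making, because the sponsor turned to de-mediation when it judged censoring open to bias, and the remedy uses variables that the plan already creates.

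**What to change.** - In Step 1, enter Part II and SBR at V_t; in Step 2, enter their g-lagged values. Replace the baseline-covariate wording in both lists. Deleting the time-varying text instead would remove the contradiction but leave current Part II unadjusted.
- Keep the t=1 rows in the propensity model with S₀ set to 0, so that `lag(g+1)S`, including `lag10S`, is 0 at t=1. Exclude baseline rows only as Step 2 outcome rows. All nine lags then have at least one interval with a propensity.
- Give the de-mediated Part III and ePD estimands one status in Table 1-2 and SAP 6.2.

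The cost is SAP wording and probably a small programming change, or none if the programs already use the lagged values; the code is not in the documents. It should be settled before unblinding. Carry-forward of missing Part II would remain a limitation.

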6.5.7 Results Summaries

The results from the MEMs performed on each of the $B \times M$ bootstrapped/imputed/ST de-mediated dataset will then be combined for overall inference using the Boot MI percentile approach (section 3.2.1 in Bartlett & Hughes, 2020).

Obtain dataset-specific mean point estimates θ_b of interest for each of the B dataset over the M imputations,

$$\bar{\theta}_b = \frac{1}{M} \sum_m \hat{\theta}_{b,m}$$

and overall mean point estimate θ over the B datasets:

$$\bar{\theta} = B^{-1} \sum_{b=1}^B \bar{\theta}_b, \text{ where } \bar{\theta}_b = M^{-1} \sum_{m=1}^M \hat{\theta}_{b,m}$$

Where $\theta_{b,m}$ represents the point estimate of the parameter of interest for a given endpoint obtained by applying the analysis model to any of the $B \times M$ datasets.

$\bar{\theta}$ corresponds to the average of the $B \times M$ parameter estimates (θ_b), and its 95% CI is derived by obtaining the 2.5% and 97.5% bootstrap percentile intervals of θ_b . Its 80% CI is derived by obtaining the 10% and 90% bootstrap percentile intervals of θ_b .

Derivation of 95% CIs and 80% CIs will use the same approach regardless of the parameter of interest, i.e. mean at single timepoint, mean slope, differences in mean at single timepoint or difference in mean slope.

Descriptive statistics

Summary tables presenting the observed mean and mean change from Baseline in ST de-mediated MDS-UPDRS Part I-III sum score, Part III subscale and Part III ePD subscore data will be produced by treatment group and visit.

Plots of observed mean and mean change from baseline over time will be produced by treatment group. These plots will include error bars (percentile intervals) and all treatment groups will be overlaid on the same plot.

Repeated measures model

A summary table presenting the estimated means and treatment effects of interest, i.e. difference in target population means at Month 12/Month 18 (based on the treatment by time interactions) and corresponding 95% CIs/80% CIs will be produced:

- UCB0599 high dose (360mg/day) and placebo,
- UCB0599 low dose (180mg/day) and placebo.

The % change relative placebo will also be included (see [section 5.3](#)).

A plot displaying the estimated ST de-mediated means and 95% CIs/80% CIs for each treatment group at each time point up to Month 12/Month 18, as well as differences in means and corresponding 95% CIs/80% CIs for Month 12/18 and will be produced.

For further details, refer to section [Section 5.3.1.4.1](#).

Slope model

A summary table presenting the estimated means and treatment effects of interest, i.e. difference in target population mean slope of progression over 12/18 months (based on the treatment by time interactions) and corresponding 95% CIs/80% CIs will be produced for:

- UCB0599 high dose (360mg/day) and placebo,
- UCB0599 low dose (180mg/day) and placebo.

A plot displaying the adjusted ST de-mediated mean slopes and 95% CIs/80% CIs for each treatment group from this model as well as differences in mean slope and corresponding 95% CIs/80% CIs will be produced.

For further details, refer to [Section 5.3.1.4.1](#).

6.6 Appendix 6: Key inclusion/exclusion criteria for the FAS definition

Participants who did not meet the key inclusion criteria stated below will be excluded from the FAS:

Protocol Criterion 1a: Study participant's age at baseline must be >39 and <76 years, i.e. Study participant must be 40 to 75 years of age inclusive, at the time of signing the informed consent.

Protocol Criterion 2a: Study participant has PD, with a diagnosis made by a neurologist according to the 2015 Movement Disorder Society criteria within 2 years of Baseline Visit (including diagnosis during Screening), at the time of signing the informed consent.

In practice, this be implemented by excluding participants with a disease duration greater than 27 months (3 months over the protocol-defined threshold).

Protocol Criterion 4b: A Screening DaT-SPECT, or a historical DaT-SPECT within 3 months of the Screening Visit (V1) that has been qualified by the central reader, shows evidence of dopamine transporter deficit per study requirements (refer to Section 4.2 of the protocol) and as determined by a central reader.

Protocol Criterion 6a: Study participant is in the ≤ 2.5 modified Hoehn and Yahr stage at Screening.

Criterion 7a. Study participant has never taken medications for the treatment of motor symptoms of PD and is not expected to require starting ST with a high likelihood in the next 6 months as far as clinical judgement allows.

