##### **Type of participant and disease characteristics**

2a. Study participant has PD, with a diagnosis made by a neurologist according to the 2015 Movement Disorder Society criteria within 2 years of Baseline Visit (including diagnosis during Screening).

---

3. The following diagnostic criteria must be met: bradykinesia AND at least ONE of the following: muscular rigidity, or resting tremor.

4b. A Screening DaT-SPECT, or a historical DaT-SPECT within 3 months of the Screening Visit (V1) that has been qualified by the central reader, shows evidence of dopamine transporter deficit per study requirements (refer to Section 4.2) and as determined by a central reader.

5a. Criterion removed.

6a. Study participant is in the  $\leq 2.5$  modified Hoehn and Yahr stage at Screening.

7a. Study participant has never taken medications for the treatment of motor symptoms of PD and is not expected to require starting ST with a high likelihood in the next 6 months as far as clinical judgement allows. These medications include:

- Levodopa
- Catechol-O-methyltransferase (COMT) inhibitors
- Dopamine agonists
- Monoamine oxidase-B (MAO-B) inhibitors
- Anticholinergic drugs
- Trihexyphenidyl
- Amantadine
- Safinamide

Exceptions to the above would be the following:

- Acute pharmacological testing for diagnostic purposes is allowed until 1 week before first Screening Visit.
- Historical treatment with symptomatic treatment (ST) for a duration of up to 1 month is allowed until 3 months before first Screening Visit (refer to details in exclusion criterion #26a).

8. Study participant has never taken part in disease-modifying treatment studies directed at NDD.

9. Study participant does not take N-acetyl cysteine or other cysteine donors or glutathione precursors on a regular basis as a food supplement.

10. Study participant is willing, competent, and able to comply with all aspects of the protocol, including follow-up schedule and biospecimen collection.

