4 POPULATIONS FOR ANALYSIS

The following analysis sets will be used:

- *All Study Participants Set (ASPS)*: All study participants who sign the ICF. Treatment assignment in the ASPS will be based on treatment received.
- *Randomized Set (RS)*: All study participants who are randomized. Treatment assignment in the RS will be based on treatment received.
- *Safety Set (SS)*: All randomized study participants who receive at least a partial dose of study medication. Treatment assignment in the SS will be based on treatment received.
- *Full Analysis Set (FAS)*: All randomized study participants who receive at least a partial dose of study medication, have at least 1 post-Baseline assessment. This is *any non-missing* post-baseline assessment, including unscheduled assessments. The FAS will be used for all efficacy analyses, and analyses will be conducted based on randomized treatment. This analysis set will exclude participants who do not meet key inclusion/exclusion criteria (see [appendix 6](#)), these will include criteria related to: age and disease duration at time of informed consent/baseline, Hoehn and Yahr stage at screening, evidence of dopamine transporter deficit (from screening DaT-SPECT) and ST status at screening.
- *Pharmacokinetic Set (PKS)*: All study participants in the Safety Set who have at least 1 observable PK measurement. The PKS will be used for PK analyses and treatment assignment in this analysis set will be based on actual treatment received.

The FAS will be used for all analyses with ICEs and other protocol deviations to be handled according to the approach specified for each estimand (see Sections 1.2). For a given endpoint, the analysis models will exclude any participant with a missing assessment at baseline for that particular endpoint.

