5.1.1 Date imputation

Partial dates may be imputed for the following reasons:

- Classification of adverse events (AEs) as treatment-emergent
- Classification of medications as prior or concomitant
- Calculation of duration of exposure
- Calculation of duration of AEs
- Calculation of Parkinson's disease duration
- Determining start/end date of ST

Imputed dates will not be shown in the listings; all dates will be displayed as reported in the database.

The following rules will be applied for partial AE and concomitant medication start dates when classifying as treatment-emergent or prior/concomitant and also for determining AE duration:

- If only the month and year are specified and the month and year of the first dose of IMP is not the same as the month and year of the start date then the 1st of the month will be used, or the date of Screening visit 1 if this is later (if the latter imputation results in an end date that is earlier than the start date, then the 1st of the month will be used).
- If only the month and year are specified and the month and year of the first dose of IMP is the same as the month and year of the start date, then the date of the first dose of IMP will be used. If this results in an imputed start date that is after the specified end date, then the 1st of the month will be used, or the date of Screening visit 1 if this is later (if the latter imputation results in an end date that is earlier than the start date, then the 1st of the month will be used).

- If only the year is specified, and the year of the first dose of IMP is not the same as the year of the start date then January 01 will be used.
- If only the year is specified, and the year of the first dose of IMP is the same as the year of the start date, then the date of the first dose of IMP will be used. If this results in an imputed start date that is after the specified end date, then January 01, or the date of Screening visit 1 if this is later will be used (if the latter imputation results in an end date that is earlier than the start date, then January 01 will be used). If the imputed date is the date of first dose of IMP then the event will be regarded as treatment-emergent or the medication as concomitant.
- If the start date is completely unknown, the start date will not be imputed.

The following rules will be applied to partial AE and concomitant medication stop dates when classifying as treatment-emergent or prior/concomitant:

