- If only the month and year are specified, then the last day of the month will be used.
- If only the year is specified, then December 31 of the known year will be used.
- If the stop date is completely unknown, the stop date will not be imputed.

If the above imputation still leads to a missing AE date:

Table 5–1: Calculation rules for duration of adverse events

Data availability	Onset date/time	Outcome date/time	Calculation rules
Complete data	D1	D2	$\text{Duration} = D2 - D1 + 1$
Start date missing	--	D2	$\text{Duration} = D2 - D0 + 1$ For a study participant in the SS, D0 is the date of first administration of IMP and for study participants who were randomized and not dosed, or for screen failures, D0 is the date of Screening Visit 1.
End date missing	D1		If the stop date is missing, duration will not be calculated.

Rules for calculating duration of exposure (UCB0599 or placebo)

For partial study medication stop dates, the last day of the month will be used if only day is missing. If the start date is missing or more than just the day is missing for the medication stop date, exposure duration will not be calculated. If partial dates are recorded for date of first and last dose of study medication this should be queried prior to applying any imputation rules.

Rules for calculating duration of Parkinson's Disease

Partial date of diagnosis dates will be imputed with the 15th of the month if only day is missing, if both day and month are missing the date will be imputed with 30th June (ie, the middle of the year).

Rules for determining start/end date of ST

Partial ST initiation dates will be imputed with the 15th of the month (if only day is missing) for the purposes of analyzing ST data (determining when ST started for ICE handling, and for calculating LEDD). This imputation rule will also apply to partial ST end dates. If month and/or year is missing, no imputation will be performed. If partial ST dates are recorded, these should be queried prior to applying any imputation rules.

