6.1.1.2 Baseline disease characteristics

The following Baseline disease characteristics will be summarized by treatment group for the SS:

- MDS-UPDRS Part I-III sum score, Part I, Part II and Part III score
- Modified Hoehn and Yahr Stage
- MoCA

- Duration of disease, will be calculated as follows:

$$\begin{aligned} \text{Duration of disease (months)} \\ = \frac{(\text{Date of first dose of IMP} - \text{Date of First Diagnosis} + 1)}{30.3} \end{aligned}$$

See [Section 5.1.1](#) for disease duration imputation rules.

For MDS-UPDRS, modified Hoehn and Yahr and MoCA, Day 1 (baseline) data will be used in this summary where available. If Day 1 data is not available, the latest pre-baseline data will be used. This data will also be listed based on the RS, by treatment group and participant.

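### A year-only diagnosis date from two calendar years before first dose, set to 30 June, pushes eligible participants dosed from about 26 September over the 27-month FAS limit

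*SAP*

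**What the plan says.** Protocol 5.1, criterion 2a, requires a diagnosis "within 2 years of Baseline Visit (including diagnosis during Screening". The protocol's own definition of the Full Analysis Set (9.1) has no eligibility exclusion. The SAP adds one (section 4, recorded as a change in 6.2), and Appendix 6 puts criterion 2a into practice by "excluding participants with a disease duration greater than 27 months (3 months over the protocol-defined threshold".

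SAP 5.1.1 gives "Calculation of Parkinson's disease duration" as one reason for imputing partial dates. For a diagnosis date, "if both day and month are missing the date will be imputed with 30th June"; if only the day is missing, the 15th of the month is used. SAP 6.1.1.2 holds the only duration formula: first dose minus diagnosis plus one day, divided by 30.3. It refers to SAP 5.1.1 "for disease duration imputation rules".

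SAP section 4 uses the FAS for all efficacy analyses and describes the exclusion as resting on "age and disease duration at time of informed consent/baseline", so the anchor date is not settled. For partial treatment-start, dosing and symptomatic-treatment dates, SAP 5.1.1 asks for a query before imputation. It asks for none for diagnosis dates.

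**The concern.** A mid-year date is a sensible central guess for a descriptive table. It becomes a problem when the result decides whether a randomised, dosed participant enters the primary analysis.

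Take a diagnosis recorded only as 2020 and a first dose on 15 November 2022. If the participant meets criterion 2a, the diagnosis fell on or after 15 November 2020, so 30 June 2020 cannot be the true date. The rule nevertheless computes a duration from it and finds the participant over the limit. The 3-month allowance in Appendix 6 is too narrow to absorb the error. At stake is the removal of eligible participants from every efficacy analysis on a date that the trial's own eligibility confirmation contradicts. Neither the covariate sensitivity analysis in SAP 5.3.1.3 nor the actual-treatment one named in SAP 5.1.2.3 is designed to bring them back.

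**Working it through.** **Inputs.** Limit: 24 + 3 = 27 months, which reproduces the plan's figure; in days, 27 × 30.3 = 818.1 (SAP Appendix 6 and 6.1.1.2). Imputed diagnosis: 30 June of the recorded year (SAP 5.1.1). Duration = (first dose − diagnosis + 1)/30.3. Planned randomised number: 450 (SAP 3).

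**Diagnosis recorded as 2020, first dose in 2022.** From 30 June 2020 to 30 June 2022 is 730 days. The last column gives the true durations possible for a participant who meets criterion 2a, from a diagnosis on 31 December 2020 up to one exactly two years before dosing (731/30.3 = 24.13).

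| First dose | Days + 1 | Imputed duration (months) | Possible true duration if eligible (months) |
|---|---|---|---|
| 25 Sep | 730 + 87 + 1 = 818 | 27.00 (just under; kept) | 20.93 to 24.13 |
| 26 Sep | 819 | 27.03 | 20.96 to 24.13 |
| 1 Oct | 824 | 27.19 | 21.12 to 24.13 |
| 15 Nov | 869 | 28.68 | 22.61 to 24.13 |
| 15 Dec | 899 | 29.67 | 23.60 to 24.13 |

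Every eligible participant in this cell dosed from 26 September on is over the limit. Where the interval contains a leap day, the window opens one day earlier (for 2019 and 25 September 2021: 731 + 87 + 1 = 819, giving 27.03).

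**Size of the imputation error.** 30 June to 31 December is 184 days, and 184/30.3 = 6.1 months, against a tolerance of 3. If only the day is missing, the 15th is wrong by at most 16 days, which the tolerance absorbs.

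**Other diagnosis years.** Previous year, latest first dose (31 December): 550/30.3 = 18.15 months, or 551/30.3 = 18.18 with a leap day. Same year: at most 185/30.3 = 6.1. Neither is ever excluded. A diagnosis three calendar years back cannot meet criterion 2a.

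**Anchor at consent.** Visit 1 falls 23 to 42 days before Baseline (Protocol 1.3). Moving 25 or 26 September by those lags puts the start of the first-dose window at 18 or 19 October (23 days) to 6 or 7 November (42 days).

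**Likely number.** Assume diagnosis dates uniform over the two years before dosing and dosing uniform over the year. The window from 26 September to 31 December has 97 days. On average 49 of the 731 eligible diagnosis days fall in the year two back: 49/731 = 6.7% of year-only participants dosed in the window. Over the whole year, 6.7% × 97/365 = 1.8%. The share of year-only dates is not in the documents. At 5%, 10%, 20% and 50%, the expected exclusions are 450 × share × 1.8% = 0.4, 0.8, 1.6 and 4.

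**The case against.** Appendix 6 does not itself say that the imputed date feeds the 27-month test. That is an inference, though a strong one: there is only one duration formula, and it refers to the imputation rules.

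Human review is built in. SAP 5.1.2.2 has analysis-set membership documented at the final data evaluation meeting before lock. SAP 5.2 lists those excluded from the FAS with the reason. Protocol 9.5.3 has important deviations identified before unblinding. A reader might infer that removal is automatic; these steps mean the documents do not support that. They do not close the gap either, because nothing tells the meeting to look behind an imputed date or lets it set the 27-month rule aside.

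A reader might also infer that all year-only participants dosed in autumn are lost. The arithmetic does not bear this out: only a diagnosis year two calendar years back is affected.

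The case may also be rare in practice. With that diagnosis year and an autumn dose, a site needs more than the year to confirm criterion 2a, so a fuller record should exist. That stands, and it is a reason to query. Finally, SAP Amendment 2 chose the central date deliberately over the longest possible duration. That is reasonable for summaries; the FAS exclusion came later, in Amendment 3.

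**Conclusion.** The concern holds in a narrow form. For a year-only diagnosis two calendar years before first dose, the SAP's rules read together place every eligible participant dosed from about 26 September to 31 December above 27 months, and so outside the FAS. With a consent anchor the window is shorter but remains.

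The conclusion rests on the imputed date being used in Appendix 6. The count, about 0.4 to 4 of 450, rests on the uniform-date assumption and an assumed 5% to 50% share of year-only dates; the documents do not show that any exist. A stronger reading would be that the primary estimate is biased or power is materially lost. The documents do not support it: the dates are fixed at or before first dose, nothing in the rule ties exclusion to outcome, and the expected number is small. This is a minor defect, worth correcting because it is avoidable.

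**What to change.** Amend Appendix 6 before database lock:

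- Query year-only diagnosis dates before applying the 27-month rule, as SAP 5.1.1 already requires for symptomatic-treatment dates.
- If a date stays year-only, do not exclude on the imputed date. Exclude only if the latest date consistent with the record gives more than 27 months, or if a criterion 2a deviation is confirmed at the blinded data evaluation meeting.
- State whether duration is measured at consent or at first dose.
- Keep the 30 June rule for descriptive summaries.

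The cost is a few lines of SAP text and a small number of queries. The downside is that a few participants with truly longer duration may stay in the FAS. The present rule also lets some through: a diagnosis on 1 January 2020 recorded as 2020 and dosed on 15 August 2022 is imputed at 777/30.3 = 25.6 months against a true 958/30.3 = 31.6. The latest-date test alone would be looser: 2020 would pass for a first dose up to 28 March 2023, when the true duration could reach 1183/30.3 = 39.0 months. It should therefore be paired with the query and the blinded deviation review.
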